Somatostatin receptor scintigraphy using [¹¹¹In-DTPA-D-Phe]-pentetreotide (Octreoscan, OCT), an analog of somatostatin, may identify gastroenteropancreatic tumors, carcinoids, and medullary thyroid carcinomas, all of which express somatostatin receptors (12). The conventional 6 mCi dose of OCT has been reported to localize ectopic ACTH production, at NIH and elsewhere (12-14). De Herder et al. reported a sensitivity of 78% for Octreoscan in patients with ectopic ACTH production (15). However, at NIH, our experience with somatostatin receptor scintigraphy using the conventional dose of 6 mCi of [¹¹¹In-DTPA-D-Phe]-pentetreotide has not been as promising. Detectability of lesions in scintigraphic studies depends not only on the size of the lesion but also on the amount of radioactivity in that lesion. Thus, in the original version of this protocol, we investigated whether a higher dose of radiopharmaceutical could lead to higher concentrations in a lesion and better visualization. In thyroid cancer, it is known that higher doses of ¹³¹I can detect more lesions than lower doses. Furthermore, investigators using high doses of [¹¹¹In-DTPA-D-Phe]-pentetreotide for therapy (180 mCi) have seen more lesions on patients' post therapy scans as compared to their diagnostic scans (16). Analysis of 27 patients with surgically-proven ectopic ACTH-secreting tumors showed a 59% sensitivity for the "low dose" (6 mCi, L-OCT). In patients who had negative L-OCT, "high dose" (18 mCi, H-OCT) had an additional 58% (7/12 patients) sensitivity (17). As a result, the project was amended in 2006 to consider the high dose Octreoscan a medically-indicated test.

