However, H-OCT delivers a substantial radiation dose, particularly when coupled with the L-OCT as is done here. In particular, the bladder receives high dose because these radiopharmaceuticals are excreted by the kidneys. (See later: concern about radiation). Thus, while the benefit-to-risk ratio has been considered acceptable because of improved localization and the high morbidity and mortality experienced by patients with this disease, a lower radiation dose would be preferable. To this end, we propose evaluation of whether the antiglucocorticoid mifepristone can improve L-OCT sensitivity in patients with active hypercortisolism. ¹¹¹In-DTPA-D-Phe]-pentetreotide binds primarily to the somatostatin receptors subtypes (sst) 2 and 5. There is a large variability in functional sst2 receptor expression in these tumors (18), which may account for failure of OCT detection of tumors. One explanation for this variability is that glucocorticoids can directly down-regulate the expression of sst2 in neuroendocrine cells *in vitro* (19-20). If this is the case *in vivo*, antagonism of glucocorticoid action would be expected to relieve this down-regulation, and possibly allow for conversion of a negative OCT to a positive study. Two patients treated with mifepristone at the NIH and in the Netherlands, who converted from a negative to a positive scan, generated this hypothesis (22). However, the interval between the scans was from 2 – 12 months. To test this hypothesis formally, we will administer mifepristone to individuals whose initial L-OCT is negative, and will obtain a second L-OCT after ten days of mifepristone 600 mg daily. This dose is expected to antagonize most glucocorticoid effect in patients with ectopic ACTH secretion.

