(c) Can the administration of mifepristone, 600 mg daily for 10 days, convert a negative standard 6 mCi OCT (L-OCT) to a subsequent positive result?

MRI

(d) Does gated chest MRI detect more lesions than routine MRI?

STUDY DESIGN AND METHODS

Standard Medical Evaluation of Cushing Syndrome

We will evaluate patients at the Clinical Center on an inpatient ward. Each subject will undergo a complete medical history, physical examination, and chemical screening tests, including acute care panel, liver function tests, thyroid function tests, complete blood count, plasma ACTH levels (30 ml of blood), and urine free cortisol. Patients also undergo measurement of diurnal cortisol in blood and saliva to confirm the diagnosis of Cushing syndrome (20 ml of blood). This is followed by a CRH stimulation test (30 ml of blood), inferior petrosal sinus sampling (IPSS; 90 ml of blood) and 8 mg overnight dexamethasone suppression test (10 ml of blood). Patients undergo MRI before IPSS: those with a mass greater than 6 mm diameter may not need IPSS, if CRH and dexamethasone suppression tests are compatible with Cushing's disease. All of these tests are performed as part of the standard evaluation of Cushing syndrome.

The initial diagnostic evaluation lasts up to 14 days. Where not limited by medical or social concerns, and where guesthouse accommodation is available, it may be performed in the outpatient/day hospital areas except for overnight stays associated with diurnal sampling. Patients whose results are consistent with Cushing's disease will be referred for transsphenoidal surgery, and will not undergo the imaging studies described below.

Patients whose evaluation indicates ectopic ACTH secretion (generally, lack of response to CRH, dexamethasone and lack of central to peripheral ACTH gradient on IPSS) will undergo standard, medically-indicated, imaging studies for localization of the tumor, including CT (neck, chest, abdomen, and pelvis), 1.5 T MRI (neck, chest, abdomen, and pelvis), and 6 mCi standard Octreoscan (L-OCT). Women will undergo a serum pregnancy test within 24 hrs before administration of any isotope.

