The research L OCT scan will be performed in the same manner as the clinical study, except that SPECT/CT of any one area will only be performed up to 2 times. All other SPECT studies of the area will be performed without CT. No clinical H-OCT study will be performed on these patients within one year of the research L OCT study.

Evaluation and treatment at the conclusion of imaging episodes

The investigators will review the results of all imaging studies at the end of each admission. Imaging results will be correlated; as is typical in standard medical care, we will not blind the reader of any conventional images to other results. However, the F-DOPA PET/CT, studies will be read without knowledge of the results of conventional MRI and CT studies. If the conventional imaging studies localize a possible tumor, the patient will undergo surgical resection, probably during a subsequent admission. If the conventional imaging studies are equivocal, or if only the research studies suggest a tumor, additional studies will be performed as clinically indicated. These studies may include repeat CT scan focused on the area of concern, venous sampling for ACTH measurement in chest or abdominal vessels, ultrasound examination, bone scan, MIBG scan, fine needle biopsy or other tests. The patient will not undergo surgery unless additional studies reveal a mass. Thus, at the conclusion of each episode of evaluation (and possible treatment), some patients with positive imaging will have surgical confirmation of the source of ectopic ACTH secretion. All others will be non-localized. These patients will receive treatment for hypercortisolism (usually medical, but adrenalectomy may be chosen), and will return to the Clinical Center to have repeated CT and MRI imaging (every 6-12 months) and repeated F-DOPA

Clinical Center to have repeated CT and MRI imaging (every 6-12 months) and repeated F-DOPA PET/CT and OCT (every 12 months).

If Cushing syndrome recurs or if patients are not cured by initial resection, patients are offered re-evaluation to localize any residual tumor or recurrence. In that case, all clinical, biochemical, and imaging tests may be repeated similar to the initial visit. Upon completion of the study, the patients are returned to the care of their referring physician.

Concern about radiation dose

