(a) *Compared to other imaging techniques, is the sensitivity and specificity of F-DOPA PET/CT higher in detecting the source of ectopic ACTH production in patients with known and unknown tumor localization?* To determine this, we will calculate the sensitivity, specificity, positive and negative values in patients with proven tumors and compare these with the results from the other modalities. Confidence intervals will be calculated and overlapping results will indicate that the modalities are similar. We cannot perform these calculations for unknown tumors, but can compare the overall percentage of tumors found of all imaged using each technique.

(b) *Does a correlation exist between F-DOPA uptake and the type of tumor, its size and proliferative activity?* To do this, we will evaluate the percent of each type of tumor that has a positive F-DOPA scan. Confidence intervals will be used to compare across tumor types. Univariate logistic regression will be performed using size and mitotic index as the variables.

(c) *Can the administration of mifepristone, 600 mg daily for 10 days, convert a negative standard 6 mCi OCT (L-OCT) to a subsequent positive result?* This will be a descriptive analysis, indicating the percentage of tumors that convert the test to a positive result. A post-hoc analysis will compare this percentage to the historical percentage of tumors that are positive on high but not low dose octreoscan.

(d) *Does gated chest MRI detect more lesions than routine MRI?* A similar approach will be used, to look at the percentage of known tumors that are detected by gated vs routine MRI and comparing confidence intervals around those values.

PHARMACEUTICAL AND RADIATION SAFETY

Pharmaceutical Information: F-DOPA

F-DOPA is a radiolabeled amino acid (^{18}F has a 109 minute half-time). It is approved by the FDA for use under IND # 35513. [name], Chief, PET Department, holds the IND. F-DOPA is produced as outlined in the IND. F-DOPA has been used in many protocols at the NIH and at other centers throughout the world. The formulation is prepared on the day of use and assayed in a dose calibrator. The total amount of F-DOPA will typically be ~2.4 mg and will not exceed 6.5 mg.

Pharmaceutical Information: [^{111}In -DTPA-D-Phe]-pentetreotide

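### Objective (c) asks whether mifepristone converts a negative Octreoscan, but an uncontrolled before/after design in patients selected for a negative first scan cannot separate a drug effect from repeat-scan variability

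*Combined protocol and SAP*

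**What the plan says.** Under Objectives, and again under Data Collection and Evaluation, the question is "Can the administration of mifepristone, 600 mg daily for 10 days, convert a negative standard 6 mCi OCT (L-OCT) to a subsequent positive result". The Introduction presents the second scan as a test of that idea: "To test this hypothesis formally, we will administer mifepristone to individuals whose initial L-OCT is negative". The second L-OCT follows ten days of drug, at least ten days after the first (Research Procedures; Octreoscan procedure).

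For the analysis of (c), Data Collection and Evaluation states: "This will be a descriptive analysis, indicating the percentage of tumors that convert the test to a positive result". It adds one comparison: "A post-hoc analysis will compare this percentage to the historical percentage of tumors that are positive on high but not low dose octreoscan". The Introduction gives that historical figure: the 18 mCi scan (H-OCT), in patients negative on L-OCT, "had an additional 58% (7/12 patients) sensitivity". The same section introduces the approaches to all four objectives as additional to McNemar's test. Justification of the number of subjects gives no sample size for the mifepristone study, for want of data.

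Repeat L-OCTs without mifepristone are also scheduled. Non-localized patients return for Octreoscan every 12 months (Evaluation and treatment at the conclusion of imaging episodes). The first and third consent categories include a 6 mCi scan at each admission (Consent Process and Documents). No analysis uses these scans for (c).

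**The concern.** The question is causal, but the design gives one group, two scans, and entry only if the first scan is negative. A patient can then stay negative or become positive; no change in the other direction can be observed. A second 6 mCi scan may be positive for reasons unrelated to the drug, such as counting statistics, bowel activity or a different reading. Blinded reading is stated for F-DOPA PET/CT but not for the second L-OCT.

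The historical H-OCT yield cannot fill the gap. It comes from a different test at three times the activity. It can suggest which strategy finds more tumors, but not whether a second L-OCT without mifepristone would have been positive.

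What is at stake is how the percentage is read. The collaborators section says the research agreement intends to develop mifepristone as an adjunct to Octreoscan. A modest conversion rate could be taken as support for that use when a second look alone might have produced part of it.

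**Working it through.** **Inputs from the protocol**
- L-OCT sensitivity, from the Introduction: "Analysis of 27 patients with surgically-proven ectopic ACTH-secreting tumors showed a 59% sensitivity". 59% of 27 is 16 patients, so p = 16/27 = 0.593.
- Historical comparator, also from the Introduction: 7/12.
- Selection: every treated patient has a negative first L-OCT.

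**Assumptions not in the documents**
- Test-retest agreement between two L-OCTs (kappa), taken from 0.9 to 0.4.
- The same positive rate on both scans.
- The number treated (10, 20 or 30).

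**Step 1. The plan's own figure.** 7/12 = 58.3%, as stated; the exact (Clopper-Pearson) 95% interval is 27.7% to 84.8%. (16/27 leaves 11 negatives, against 12 in this denominator, so the two figures may come from different sets. Nothing below depends on that.)

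**Step 2. Conversion with no drug effect.** With equal marginals, let b be the probability of negative then positive. Then kappa = 1 − b / [p(1 − p)], so b = p(1 − p)(1 − kappa). Dividing by the probability of a negative first scan, 1 − p, gives

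c = P(second positive | first negative) = p(1 − kappa).

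With p = 0.593, the chance of at least one conversion in 10 is 1 − (1 − c)^10, and the chance of six or more is a binomial tail:

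| Assumed kappa | c | At least 1 of 10 | 6 or more of 20 | 6 or more of 30 |
|---|---|---|---|---|
| 0.9 | 6% | 46% | 0.1% | 0.7% |
| 0.8 | 12% | 72% | 2% | 14% |
| 0.6 | 24% | 93% | 33% | 75% |
| 0.4 | 36% | 99% | 77% | 98% |

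**Step 3. Sensitivity to p.** The 59% comes from surgically proven tumors. If treated patients with occult tumors are counted, p is lower. At an assumed p = 0.30, c is 0.30 × 0.1 = 3%, 0.30 × 0.2 = 6%, 0.30 × 0.4 = 12% and 0.30 × 0.6 = 18% for the same four kappas. With kappa = 1, c is zero.

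**Step 4. McNemar's test.** The exact test compares negative-to-positive with positive-to-negative pairs. Selection fixes the second count at zero, so with k conversions the two-sided p-value is 2 × 0.5^k. For k = 5 this is 0.0625; for k = 6 it is 0.031. It depends neither on how many patients were scanned nor on why the scans changed. The last two columns of the table are therefore the probabilities of a nominally significant result with no drug effect.

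**The case against.** The strongest reply is that (c) is a small pilot estimate. It is labelled descriptive, has no success threshold, and the protocol admits it has no data for sizing. A reader might infer that the plan credits every conversion to mifepristone; it does not say so. That stands. But the question is causal, the Introduction calls the test formal, and McNemar's test is introduced for all four objectives, so the label alone does not settle how the percentage will be read.

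A reader might also infer that the bias must always favour mifepristone. The documents do not support that. Selection on a negative scan pushes that way, but the research scan caps SPECT/CT of any one area at two, and extra delayed images are mentioned only for clinical scans. Both could make the second scan less likely to be positive. The short interval limits tumor change, and other medical treatment for hypercortisolism is excluded meanwhile. Pathology as reference standard removes some spurious positives, though not a real tumor missed once and seen by chance the second time.

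A third tempting step is to treat the conversion rate in repeat L-OCTs without mifepristone as an upper bound on spontaneous conversion, and to credit the drug only with the excess. That fails too. The roughly 12-month gap and treatment of hypercortisolism may raise this rate; on the protocol's own hypothesis, lower cortisol could restore receptors. In the other direction, L-OCT-negative patients who do not get mifepristone go to H-OCT, and those localized can leave for surgery, so the patients who remain may have harder tumors. The net direction is unknown. Hypercortisolemic pairs may be few, since the consent section expects most patients to be hypercortisolemic at only one visit.

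**Conclusion.** The concern holds as a limit on what (c) can conclude. Nothing in the plan separates a mifepristone effect from a second look, and the historical H-OCT comparison does not do so. The documents cannot fix the size: about 6% to 36% conversion without drug effect at p = 0.593 and kappa 0.9 to 0.4, less if the positive rate in treated patients or on the second scan is lower, and near zero if L-OCT is almost perfectly repeatable. The McNemar result needs no assumption about kappa: given selection on a negative first scan, six conversions reach p = 0.031 whatever their cause. The documents do not show that mifepristone is ineffective or that any observed conversion would be spurious.

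**What to change.** In Data Collection and Evaluation, item (c):

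1. Report the percentage with an exact 95% confidence interval, under the label *conversion on repeat scanning after mifepristone*.
2. State that the uncontrolled design does not by itself attribute conversion to the drug.
3. State that McNemar's test is not applied to (c), because selection makes one discordant cell zero.
4. As exploratory context only, tabulate negative-to-positive conversion between successive 6 mCi L-OCTs done without mifepristone under this protocol. Give the number of pairs, an exact interval, the time between scans, and cortisol status at each scan.
5. State that the direction of bias in this reference is unknown, with the reasons on each side. Do not call it an upper bound or use it as an attribution threshold.

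The cost is one tabulation of scans scheduled anyway and a few sentences. No scan, radiation exposure or clinical rule changes. The downside is that the reference pairs may be few and imperfectly comparable, and that the conclusion on (c) becomes more cautious. If too few pairs exist, items 1 to 3 still correct the inference.

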We found that F-DOPA PET substantiated a lesion seen on CT and/or MRI scan in 6 of 11 patients, including some with questionable results on conventional imaging. We amended the protocol in 2008 to administer carbidopa, 200 mg, one hour before the study. [name] has found that this strategy improves tumor detection of pheochromocytoma, presumably by inhibiting decarboxylation of the tracer. This amendment will now allow us to perform FDOPA PET/CT, which was not available previously.

The project was amended in 2004 regarding the routine chest MRI scans. We initially obtained images on a 0.5 T magnet using, using STIR, T1 and T2 images. Subsequently a 1.5 T magnet replaced the lower strength magnet and STIR images were not obtained. Recently a 3.0 T magnet has become available with image acquisition gated to the EKG R-R interval so that artifact from cardiac motion is reduced. Our collaborator [name] has performed T1 and T2 sequences using this approach with excellent resolution of mediastinal and chest structures. Increased strength of magnetic field compared to conventional 1.5T MRI allows for a stronger signal and therefore improved signal to noise ratio. Free breathing techniques are used to avoid breath holding, which may be difficult for those patients with volume overload. The combination of higher signal and decreased motion artifacts should significantly improve resolution allowing for better delineation of small lesions that may be responsible for ectopic ACTH production. To test this, we have added these sequences.

We wish to clarify the use of chest CT scans, as the available modalities have changed. A “surgical chest protocol CT” (which involves thin (1-2mm) cuts throughout the thorax) will be obtained at each visit.

For the initial imaging, gated “cardiac CT” will be obtained as well to look for retrocardiac lesions that can be obscured by non-gated routine CT. However, because of the amount of radiation, we will obtain this scan only at the initial visit, unless there is a subsequent clinical suspicion of a retrocardiac lesion.

OBJECTIVES

Specific questions to be addressed:

F-DOPA PET/CT

(a) Compared to other imaging techniques, is the sensitivity and specificity of F-DOPA PET/CT higher in detecting the source of ectopic ACTH production in patients with known and unknown tumor localization?

(b) Does a correlation exist between F-DOPA uptake and the type of tumor, its size and proliferative activity?

Octreoscan

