Patients without active hypercortisolism in whom the standard Octreoscan is negative (or those ineligible for the mifepristone study) will undergo H-OCT. Because of interference we will wait at least one week after dosing a low dose Octreoscan before doing a H-OCT. The IRB previously agreed that this would be a medically indicated procedure in these patients. However, because it adds significantly to the cumulative radiation exposure, we have decided to limit this to three scans at intervals of at least one year.

The duration of standard imaging studies is about 10-15 minutes for either CT of the neck, chest, abdomen, or pelvis and 1-2 hours for either MRI of the pituitary, chest, abdomen, or pelvis, and 1-3 hours for Octreoscan (see below).

Research Procedures

Eligible patients with active hypercortisolism will receive the mifepristone-L-OCT combination as a research study (see below). Patients will undergo F-DOPA PET/CT as a research study, up to two studies with an interval of at least 12 months. Patients may undergo imaging before or after treatment of ectopic Cushing syndrome (if they have evidence of active ectopic ACTH secretion). Because of interference and to allow for administration of mifepristone, we will wait at least ten days after dosing a low dose Octreoscan before doing a second L-OCT. A gated chest MRI will be obtained using a 3 Tesla magnet with T1 and T2 sequences. Blood will be collected into one heparin and serum tube and an aliquot of urine will be retained for additional clinical or future research studies related to hypercortisolism. As an example, we previously studied the utility of pro-calcitonin using research samples collected under another protocol (39). Patients will be asked to consent to the future use of tumor samples. If they consent to such use, samples may be used in the future, with identifiers, for studies not described here, without obtaining new informed consent. Only studies related to Cushing's syndrome or the biology of tumors would be undertaken.

F-DOPA PET/CT procedures

The research team is responsible for ensuring that PET-specific regulations and procedures are followed.

Patients are studied in the PET Department scanning facility at the Clinical Center after a minimum of 6 hours fasting. A plastic catheter is inserted into an arm vein. Patients receive carbidopa, 200 mg, orally 60 minutes before the scheduled injection of F-DOPA.

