The IRB previously approved an accrual ceiling of 202 for the high dose octreoscan component. That component is no longer a part of the protocol. Eighty-nine patients have enrolled in the protocol. F-DOPA PET was positive in 8 of 17 patients with known tumors and high dose Octreoscan was positive in 7 of 12.

Given these encouraging results, we propose performing F-DOPA in a total of at least 30 patients. The current results imply an estimated success rate of about 55% for each modality; the plausible range for the true success rate ranges from about 26 to 80% using a 95% confidence interval, a very broad range.

Studying a total of 30 patients will allow us the possibility of precluding a true success rate of under 20% (with 95% confidence) if we were to see no additional successes. If there are additional successes in the additional patients the confidence interval for what the true probability of success could be will still be fairly broad. Since limited patients have been evaluated using F-DOPA, we ask that the overall accrual ceiling remain intact and that it be altered based on annual reports of the results. Additionally, we have essentially no data on which to base a sample size calculation for the mifepristone study, and would recalculate accrual limits when such data are available.

Data Collection and Evaluation

Staff in the Departments of Radiology will evaluate the conventional studies. [name] reviews the F-DOPA PET/CT without knowledge of the results of other localization studies. [name] reviews all studies. Data are maintained by the NICHD Clinical Trials DataBase.

The study will be analyzed in collaboration with [name] (Clinical Center Statistics Center). Data are collected and analyzed with regard to the sensitivity, specificity, accuracy, and predictive value for each scan being evaluated. The exploration and pathologic analysis is used as the reference standard. McNemar's test for evaluating paired data will be used (40). In addition to McNemar's test, other approaches to evaluation of the four objectives are below:

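### Objective (d) compares a chest-only 3 T gated MRI with an undefined routine MRI over all known tumors, so non-thoracic tumors dilute or can reverse the chest result

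*Combined protocol and SAP*

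**What the plan says.** - **Question.** Objective (d) asks: "Does gated chest MRI detect more lesions than routine MRI". The region of the routine MRI is not stated.
- **Analysis.** Under Data Collection and Evaluation, item (d) follows an approach similar to the preceding items: "to look at the percentage of known tumors that are detected by gated vs routine MRI", then "comparing confidence intervals around those values". Item (a) reads overlapping intervals as showing that modalities are similar.
- **Paired test.** The same section states "McNemar's test for evaluating paired data will be used (40" and presents the item-by-item approaches as additions to it for all four objectives. No significance level or sample size is given for (d).
- **Gated scan.** Research Procedures: "A gated chest MRI will be obtained using a 3 Tesla magnet with T1 and T2 sequences".
- **Standard scan.** Standard Medical Evaluation of Cushing Syndrome lists "1.5 T MRI (neck, chest, abdomen, and pelvis" among the medically indicated studies.
- **Rationale.** The Introduction begins this topic with "The project was amended in 2004 regarding the routine chest MRI scans", reports "excellent resolution of mediastinal and chest structures" for the gated approach, and attributes the expected gain jointly to higher signal and less motion artifact.
- **Tumor sites.** The Introduction names pancreatic islet cell tumor, medullary thyroid cancer and pheochromocytoma among the most common sources. The reference standard is exploration and pathology, with no restriction on site.

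**The concern.** A scan limited to the chest cannot show a pancreatic, thyroid or adrenal tumor. Scoring it on all known tumors mixes two questions: how well it sees chest lesions, which is what the Introduction says is being tested, and how many tumors lie in the chest, which says nothing about the scan.

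The effect depends on a comparator that the plan leaves open. With routine chest MRI, non-thoracic tumors are misses for both scans and only dilute the contrast. With the four-region MRI, those that the routine scan detects become discordant pairs against gated MRI. The choice could be made after the data are seen, and it can change the direction of the answer.

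The decision rule is a second weakness. Both scans are done in the same patients, so two separate intervals ignore the pairing. Reading overlap as similarity can conflict with the paired test in the same section, and the plan does not say which governs.

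**Working it through.** The plan gives no figure for (d) to reproduce: no sample size, power, MRI detection rate or thoracic share. The inputs below are assumptions.

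**1. All-tumor difference.** Let t be the thoracic share, g the gated sensitivity in the chest, r the routine sensitivity in the chest, and q the routine sensitivity elsewhere. Gated sensitivity elsewhere is 0.

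- Thoracic tumors only: g - r
- All tumors, routine chest MRI: t(g - r)
- All tumors, four-region MRI: t(g - r) - (1 - t)q

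With g = 80% and r = 60%, the true chest difference is +20 points. Differences in points (gated minus routine):

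| Thoracic share t | Routine chest MRI | Four-region, q = 30% | Four-region, q = 60% |
|---|---|---|---|
| 100% | +20 | +20 | +20 |
| 90% | +18 | +15 | +12 |
| 80% | +16 | +10 | +4 |
| 70% | +14 | +5 | -4 |
| 60% | +12 | 0 | -12 |
| 50% | +10 | -5 | -20 |

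Example: t = 0.7, q = 0.6 gives 0.7 x 0.20 - 0.3 x 0.60 = 0.14 - 0.18 = -0.04. With q = r the formula reduces to tg - r, so the sign changes at t = r/g = 0.60/0.80 = 75%. With q = 30% it changes at t = 60%.

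If the scans are equally good in the chest (g = r = q = 50%), the four-region reading still gives -5, -10, -15 and -20 points at shares of 90, 80, 70 and 60%.

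**2. The same in counts.** Assume 30 known tumors, 20 of them thoracic. Routine MRI finds 12 of the 20; gated MRI finds those 12 and 4 more. On the four-region reading routine MRI also finds 6 of the 10 non-thoracic tumors. P values are exact two-sided McNemar.

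| Denominator and comparator | Gated | Routine | Gated-only v routine-only | p |
|---|---|---|---|---|
| All tumors, four-region | 16/30 = 53% | 18/30 = 60% | 4 v 6 | 0.75 |
| All tumors, routine chest | 16/30 = 53% | 12/30 = 40% | 4 v 0 | 0.125 |
| Thoracic only, chest field | 16/20 = 80% | 12/20 = 60% | 4 v 0 | 0.125 |

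Rows 2 and 3 have the same p: tumors missed by both scans are concordant. Only the percentages and their difference change, from 20 to 13 points. Row 1 reverses the direction.

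**3. Interval overlap against the paired test.** Assume 20 thoracic tumors: 8 seen by both scans, 8 by gated only, 1 by routine only, 3 by neither. Gated finds 16/20 = 80% (95% Clopper-Pearson 56-94%) and routine 9/20 = 45% (23-68%). The intervals overlap, so the approach in (a) would call the scans similar. Exact McNemar on 8 v 1 gives p = 2 x (1 + 9)/2^9 = 20/512 = 0.039. The paired difference is (8 - 1)/20 = 35 points.

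**The case against.** The strongest reply is that the intended comparison is plainly chest to chest. The objective names gated chest MRI, the Introduction frames the change as one to routine chest MRI scans, and scan durations are given by region, so a routine chest MRI exists as its own examination. On that reading no reversal can occur and McNemar's test is unaffected. This stands, and it rules out some stronger inferences:

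- **That the plan sets the four-region MRI as comparator.** It does not; routine MRI is undefined in (d). The section on adverse events and monitoring also lets teams leave regions unscheduled, so four-region coverage is not universal.
- **That every non-thoracic tumor becomes evidence against gated MRI.** Each lowers the gated percentage, but only those found by routine MRI become adverse discordant pairs.
- **That no paired analysis is planned.** McNemar's test covers all four objectives. The problem is the overlap rule placed beside it.
- **That the plan claims to isolate gating.** The Introduction credits field strength and gating together. The objective's wording is merely looser than the rationale.

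The magnitudes are also assumed, and the 30 tumors are illustrative: the only planned 30 in the document refers to patients having F-DOPA.

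What the reply does not remove is that, as written, the denominator includes tumors outside the gated field. Even the favorable reading shrinks the difference, and nothing in (d) prevents the other reading.

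**Conclusion.** The point holds as a gap in the specification of (d), with two consequences.

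First, the unrestricted denominator makes each non-thoracic tumor a gated miss. With routine chest MRI as comparator, the difference is multiplied by the thoracic share (20 points becomes 13 when 20 of 30 tumors are thoracic) and its direction is safe. With the four-region MRI, a true 20-point chest advantage disappears at a thoracic share of 75% if routine MRI finds 60% of tumors outside the chest, or at 60% if it finds 30%. These figures rest on assumed sensitivities and shares; the documents cannot show how large the effect would be in this trial.

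Second, comparing separate intervals can contradict the planned McNemar test, as 16/20 against 9/20 with discordant pairs 8 v 1 shows.

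The documents do not support saying that (d) is certain to be biased against gated MRI or that its direction will reverse.

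**What to change.** Amend objective (d) and its analysis as follows:

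1. Limit the analysis to patients with a pathology-proven thoracic tumor who had both scans in the same admission. MRI is repeated every 6 to 12 months in non-localized patients, so the pair must be defined.
2. Define the comparator as 1.5 T routine chest MRI, and score only the chest field of the routine examination.
3. Base the conclusion on the planned McNemar test in its exact form and on the paired difference in detection with its confidence interval, in place of interval overlap.
4. Word the conclusion as 3 T gated versus 1.5 T routine chest MRI, because field strength and gating change together.

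The cost is a few sentences and no extra scans. Fewer tumors are analysed, but those dropped carry no information on the chest question.
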